Appendix 4. Haybittle-Peto Interim Accept/Reject Boundary

Appendix 5. Tables and Figures for Data Presentation

Figure 1. Study Recruitment Consort Flow Diagram

[figure not shown]

Figure 2. Number of Participants Randomized vs Expected

[figure not shown]

Table 1. Summary of Screening, Consenting, and Randomization by Site

Categories	Buffalo	Cleveland	Dallas	Gaines-ville	Houston	Little Rock	Port-land	Tampa	Loma Linda	Minne-apolis	Ashe-ville	Palo Alto	Pitts-burg	San Fran	Seattle	Long Beach	Total
Number of Subjects Screened																	
Number of Subjects Excluded for Consent																	
Ineligible for Consent																	
Unable to Consent																	
Unable and/or Unwilling to Follow Protocol																	
Number of Subjects Consented																	
Percent of Subjects Consented (over Eligible for Consent)																	
Number of Subjects Excluded for Randomization																	
Ineligible for Randomization																	
Eligible for Randomization, but Not Randomized																	
Number of Subjects Randomized																	
Percent of Subjects Randomized (over Eligible for Randomization)																	

Table 2. Reasons of Ineligibility for Consent and Consent Information by Site

Categories	Buffalo	Cleveland	Dallas	Gaines-ville	Houston	Little Rock	Port-land	Tampa	Loma Linda	Minne-apolis	Ashe-ville	Palo Alto	Pitts-burg	San Fran	Seattle	Long Beach	Total
Veterans Screened																	
Not Veteran age 18 years or older																	
No Eligible Operation, no																	

history of CVD, IHD, or PAD																
No Eligible Operation, with history of CVD																
No Eligible Operation, with history of IHD																
No Eligible Operation, with history of PAD																
No Eligible Operation, with history of CVD and IHD																
No Eligible Operation, with history of CVD and PAD																
No Eligible Operation, with history of IHD and PAD																
No Eligible Operation, with history of CVD, IHD, and PAD																
Eligible General Operation, no history of CVD, IHD, or PAD																
Eligible Vascular Operation, no history of CVD, IHD, or PAD																
COVID-19 Positive During Pre-Screening																
Veterans Ineligible for Consent (% over Screened)																

Veterans Eligible for Consent (% over Screened)																
Veteran unable to consent (% over Screened)																
Veteran unable and/or unwilling to follow protocol (% over Screened)																
Veterans Consented (% over Eligible)																

Table 3. Reasons of Ineligibility for Randomization by Site

Categories	Buffalo	Cleveland	Dallas	Gaines-ville	Houston	Little Rock	Port-land	Tampa	Loma Linda	Minne-apolis	Ashe-ville	Palo Alto	Pitts-burgh	San Fran	Seattle	Long Beach	Total
12. Veteran with known history of hereditary anemias (% over Consented)																	
13. Veteran with known history of hereditary bleeding disorders (% over Consented)																	
14. Veteran with prior history of adverse reaction to blood administration (% over Consented)																	
15. Hemodynamically unstable or in cardiogenic shock																	

(% over Consented)															
16. Veteran participating in another interventional trial (% over Consented)															
17. Veteran is a prisoner or in custody of law enforcement (% over Consented)															
18. Prior randomization in CSP #599 (% over Screened)															
19. Pregnancy in female Veterans (% over Consented)															
22. RCRI Class not available (% over Eligible for Randomization)															
23. Index surgery not performed as planned (% over Screened)															
24. Hb did not go below 10gm/dl within 15 days (% over Screened)															
COVID-19 Positive After Consent but Before Randomization															
Number of Participants ineligible for randomization (% over Total Consented)															
Number of eligible															

Participants randomized																	
Number of eligible Participants randomized (% over Total Screened)																	
Number of eligible Participants randomized (% over Total Consented)																	
Number of eligible Participants randomized (% over Total Eligible)																	

Table 4. Reasons of Eligible Participants Not Randomized by Site

Categories	Buffalo	Cleveland	Dallas	Gaines-ville	Houston	Little Rock	Port-land	Tampa	Loma Linda	Minne-apolis	Ashe-ville	Palo Alto	Pitts-burgh	San Fran	Seattle	Long Beach	Total
Number of Participants Eligible for Randomization who were NOT Randomized																	
Eligibility status changes (e.g., died, treatment plan changed, etc.)																	
Participant changed mind after consent signed																	
Investigator/Surgeon changed mind after participant signed consent																	

Site surgeon concerned about resources needed for on-site follow-up (cost, time, etc.)																
No reliable method of follow-up contact with the participant (e.g., no phone, etc.)																
Primary reason participant preferred non-enrollment																
Primary reason surgeon preferred non-enrollment																
- Surgeon prefers restrictive transfusion for participant																
- Surgeon prefers liberal transfusion for participant																
- Surgeon believes participant has too short of life expectancy to be included																
- Surgeon believes participant is too high of a medical risk to be included																
- Reason other than transfusion preference																
Other Reason																

Table 5. Participant Disposition by Sites for All Randomized Participants (ITT)

Status	Buffalo	Cleveland	Dallas	Gainesville	Houston	Little Rock	Portland	Tampa	Loma Linda	Minneapolis	Asheville	Palo Alto	Pittsburgh	San Fran	Seattle	Long Beach	Total

Participant Study Status - Randomized Ppts																			
Completed																			
Discontinued																			
Reason for Termination																			
Participant completed study																			
Participant voluntarily withdrew																			
Participant lost to follow- up (location unknown)																			
Participant became pregnant																			
Participant was incarcerated																			
Administrative termination (e.g., non- compliance)																			
Participant relocated																			
Other																			
SAE other than death																			
Participant died																			

Table 6. Participant Disposition by Intervention Group for All Randomized Participants (ITT)

Status		Liberal	Restrictive	Total
Participant Study Status - Randomized Ppts	n			
Completed	n (%)			
Discontinued	n (%)			
Reason for Termination	n			
Participant completed study	n (%)			
Participant voluntarily withdrew	n (%)			
Participant lost to follow-up (location unknown)	n (%)			
Participant became pregnant	n (%)			
Participant was incarcerated	n (%)			
Administrative termination (e.g., non-compliance)	n (%)			
Participant relocated	n (%)			
Other	n (%)			
SAE other than death	n (%)			
Participant died	n (%)			

Table 6.1. List of Participants Who Are Administratively Terminated

Center number	Participant ID number	Group	Termination Date	Details

Table 6.2. List of Participants Whose Termination Reasons Are Listed As ‘Other’

Center number	Participant ID number	Group	Termination Date	Reason Termination

Table 7. Summary of Protocol Deviations by Intervention and Overall

Type		Liberal (n=)	Restrictive (n=)	Total (n=)
Total Number of Deviations	n			
SAE not reported	n (%)			
SAE reported late or SAE Follow-Up reported late	n (%)			
Did not follow instructions from IRB or other review bodies/committees	n (%)			
Confidentiality or privacy breach	n (%)			
Loss of source documents/samples/source media	n (%)			
Ineligible participant enrolled	n (%)			
Participant in more than one simultaneous interventional trial	n (%)			
Informed Consent/HIPAA documentation completed incorrectly	n (%)			
Informed Consent/HIPAA documentation is incomplete	n (%)			
Informed Consent/HIPAA not obtained prior to study procedures	n (%)			
Used incorrect informed consent/HIPAA version	n (%)			

Required study procedure not performed per protocol	n (%)			
Study activities performed by inappropriate personnel	n (%)			
Other (specify under Details of deviation)	n (%)			
Participant assigned to restrictive group was transfused with Hb above 7gm/dL	n (%)			
Participant assigned to liberal group was NOT transfused when Hb below 10gm/dL	n (%)			
Evidence of willful or knowing misconduct on the part of the study team	n (%)			
Participant repeated deviation with study requirements	n (%)			
Visit 30/90 outside of window	n (%)			
Transfusion outside of window/late	n (%)			
Labs/EKG on form 6 required for this date but not done	n (%)			
Hb on Form 3 required for date but not done	n (%)			
Hb used for Randomization trigger had batch draw time recorded outside of eligibility window but actual draw time was within eligibility window	n (%)			
Hb done after Randomization had batch draw time recorded outside of required window but actual draw time was within window	n (%)			
Transfusion Protocol deviation not covered by other Transfusion-specific Deviation Codes	n (%)			

Table 8. Approved Transfusion Protocol Halting by Site

	Buffalo	Cleveland	Dallas	Gaines-ville	Houston	Little Rock	Port-land	Tampa	Loma Linda	Minne-apolis	Ashe-ville	Palo Alto	Pitts-burgh	San Fran	Seattle	Long Beach	Total
1. Rapidly Bleeding (Form 4 Q9)(% over # Form 4 submitted)																	
2. Adverse Reaction During Transfusion (Form 4 Q10)(% over # Form 4 submitted)																	
3. Transfusion protocol stopped after MI; participant was transfused per attending (Form 8 Q3)(% over # Form 8 submitted)																	
4. Transfusion protocol continued after MI (Form 8 Q3)(% over # Form 8 submitted)																	
Sum of rows 1-3																	

(% over # Form 4 submitted)																	
Ppts with >=1 event in rows 1-3 (% over # Ppts with >=1 Form 4 submitted)																	

Table 9. Summary of Transfusion-Related Protocol Deviations by Site

	Buffalo	Cleveland	Dallas	Gaines-ville	Houston	Little Rock	Port-land	Tampa	Loma Linda	Minne-apolis	Ashe-ville	Palo Alto	Pitts-burgh	San Fran	Seattle	Long Beach	Total

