If during the course of the initial transfusions, any routine, non-protocol required hemoglobin check shows that Hb is past the target threshold prior to administering the total number of units indicated by the protocol, transfusion may be stopped. (example: participant assigned to the Liberal arm and has Hb less than 7.5 is, per protocol, to receive three units of PRBCs. If after the second unit, a Hb check reveals Hb greater than or equal to 10, then a third unit of PRBC is not necessary.)

For Hb values that are suspected to be incorrect (i.e., artificially low or high in the context of the participant's clinical setting), order a repeat Hb within 6 hrs. of last lab to confirm values prior to initiating transfusion.

A participant in either group may be transfused at any time without an Hb level if there is evidence of rapid bleeding (e.g. brisk gastrointestinal bleeding or suspected intraabdominal bleeding after major aortic repair) and the physician believes emergency transfusion is needed.

Furthermore, if a participant develops signs or symptoms of a possible transfusion reaction, which are estimated to occur in approximately 1% of transfused patients, the transfusion will be stopped immediately and hospital policies must be followed with respect to reporting of blood transfusions and obtaining any applicable required blood and/or urine specimens for hospital testing. The transfusion strategy protocol may be reinstated with a different unit of blood after the participant's condition has stabilized or if it is determined that the participant's signs or symptoms were probably not related to a possible blood transfusion. In the uncommon event that more than $\frac{3}{4}$ of a unit of blood is transfused prior to halting of the transfusion, then the $\frac{3}{4}$ of a unit may be considered a full unit of blood. A different unit of blood need not be transfused to fulfill the initial 1 unit requirement. The transfusion protocol may be continued as required.

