Relatedness involves an assessment of the degree of causality (attributability) between the study intervention and the event. Site investigators will be asked to provide an assessment of relatedness. The assessment provided by the site investigator is part of the information used by the sponsor to determine if the adverse event presents a patient safety concern and/or requires regulatory reporting. Pursuant to CSP Global SOP 3.6, a SAE is deemed to be associated with the use of a study drug/device if “there is a reasonable possibility that the experience may have been caused by the drug/device or by participation in the trial.” Thus, all SAEs with a reasonable causal relationship to the investigational treatment should be considered “possibly related” or “related.” A definite relationship does not need to be established but there must be some evidence to suggest a causal relationship between the investigational treatment and the adverse event (21 CFR 312.32). The following levels of relatedness will be used in this trial:

- Not attributed to a study intervention
- Possibly attributed to a study intervention
- Attributed to a study intervention

D. Collection of Safety Information

Given the large number of comorbidities expected in the study population and the high-risk operative procedures these patients will be undergoing, it is anticipated that a large number of AEs will be observed, most of which will not be related to the study intervention. For this reason, the study will only collect reports of Serious Adverse Events (SAEs).

All SAEs, whether related or unrelated to the treatment interventions, will be recorded and reported in an expedited fashion. Assessment of relatedness for SAEs is described above. Unexpected serious adverse events that are attributed or possibly attributed to a study intervention will be managed as provided in CSP Global SOP 3.6.

Directions on how to complete the Serious Adverse Event Form will be detailed in the Operations Manual. Sites are required to report each SAE to the Sponsor within 3 calendar days from the time the site investigator becomes aware of it. The PCC Study Pharmacist will complete a safety and regulatory review of all SAEs. All investigators will be notified of any new hazards or other trends involving patient safety as provided in Global SOP 5.3.

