6.2. Study Adherence

The following tables will be presented:

- Summary of protocol deviations by intervention (Table 7).
- Summary of approved transfusion protocol halting by site (Table 8).
- Summary of transfusion-related protocol deviations by site (Table 9).

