8. SAFETY ANALYSES

All safety analyses will be done for the safety population and reported in tabular forms. These analyses include serious adverse events and laboratory measurements.

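### Approved halts of the transfusion protocol, including non-serious transfusion reactions, have no planned table by arm, and one Table 8 percentage mixes two forms

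*SAP*

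**What the plan says.** Protocol XII.C names three approved instances of halting the transfusion strategy: rapid bleeding, an adverse reaction to transfusion, and a post-randomization MI. It classes every other departure as a violation.

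The SAP reports the approved instances in one place. Section 6.2 lists it as "Summary of approved transfusion protocol halting by site (Table 8", and the shell is headed "Table 8. Approved Transfusion Protocol Halting by Site". The columns are 16 sites and a Total. The reaction row is "2. Adverse Reaction During Transfusion (Form 4 Q10)(% over # Form 4 submitted". The post-MI row uses another form: "3. Transfusion protocol stopped after MI; participant was transfused per attending (Form 8 Q3)(% over # Form 8 submitted". Below these, one line sums rows 1 to 3 as a percentage of Form 4s, and the last line is "Ppts with >=1 event in rows 1-3 (% over # Ppts with >=1 Form 4 submitted".

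On harms, Protocol XI.D says "the study will only collect reports of Serious Adverse Events (SAEs". SAP section 8 says of the safety analyses: "These analyses include serious adverse events and laboratory measurements". Protocol X expects "signs or symptoms of a possible transfusion reaction, which are estimated to occur in approximately 1% of transfused patients" and requires the transfusion to be stopped when this happens.

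**The concern.** The arms differ in how readily blood is given, so a transfusion reaction is a direct harm of the strategy that gives more. A reaction that stops a transfusion but is not serious is recorded on Form 4 and does not reach the SAE tables. If its only display pools the arms, the final report contains no between-arm figure for it.

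Rapid bleeding raises a different issue. Protocol X lets either arm be transfused without an Hb level in that case. In the restrictive arm this narrows the contrast between strategies, so a reader of a null result would want to see it by arm.

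The summed line is a separate, smaller fault: its percentage counts events from one form over the number of another form.

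**Working it through.** **1. Where each approved event appears.** The shells in SAP Appendix 5 were read against SAP 6.2 and section 8.

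| Output | Layout | Approved halts shown? |
|---|---|---|
| Table 7, protocol deviations | by arm | No row for any of the three, consistent with Protocol XII.C, which does not class them as violations |
| Table 8, approved halting | 16 sites + Total | Yes, all three, arms pooled |
| Table 9, transfusion deviations | by site | No; it does carry units transfused |
| Table 29, SAEs | by arm | Only reactions that qualify as SAEs |
| Table 31, laboratory values | by arm | No |

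Non-serious reactions, rapid-bleeding transfusion and post-MI halts therefore appear in Table 8 and have no row in a by-arm table.

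**2. Denominators in Table 8.** Rows 1 and 2 are per Form 4. Rows 3 and 4 are per Form 8. The summed line adds rows 1 and 2 (Form 4 events) to row 3 (Form 8 events) and divides by the number of Form 4s. Part of the numerator is not drawn from the denominator, so the result is not a proportion of anything. The last line counts participants, with the three kinds of event merged.

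**3. The plan's own figure for arm size.** Inputs from Protocol XVI.B: 30% v 22.5%, two-sided 5%, power 90%, dropout 5%. The pooled-variance formula for two proportions is

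n per arm = [z(0.975)·√(2·p̄·(1−p̄)) + z(0.90)·√(p1(1−p1) + p2(1−p2))]² / (p1 − p2)², with p̄ = 0.2625.

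This gives 722 per arm, 1444 in total. 1444 / 0.95 = 1520, or 760 per arm. The stated figures reproduce exactly.

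**4. Expected number of participants with a reaction.** Inputs: 1% of transfused patients (Protocol X) and 760 per arm. The share of each arm transfused is not in the documents. It is assumed to be 90-100% (liberal) and 10-50% (restrictive).

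Expected = 760 × share transfused × 0.01

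- Liberal: 760 × 0.90 × 0.01 = 6.8; 760 × 1.00 × 0.01 = 7.6
- Restrictive: 760 × 0.10 × 0.01 = 0.8; 760 × 0.50 × 0.01 = 3.8
- Difference per participant randomized: 0.90% − 0.50% = 0.4 points, up to 1.00% − 0.10% = 0.9 points
- Per participant transfused: 1% in both arms, by construction

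The last two lines show why the denominator matters in a by-arm table. Under these assumptions the whole difference comes from how many participants are transfused. A percentage of those transfused would not show it, and a percentage of those randomized would. A percentage of forms would not be expected to show it either, since the arm with more transfusions also has more forms.

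**5. Could it be tested?** Exact enumeration of the binomial outcomes over the same assumed range gives two-sided 5% power of about 9% to 57% (Fisher) or 14% to 72% (Pearson). That is too low for a formal test to be useful.

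**The case against.** The strongest reply is that much of the relevant harm and adherence is already compared by arm.

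- Serious reactions are in Table 29 by MedDRA term, and Protocol XVII.E gives the DMC closed session SAEs by arm and relatedness.
- Protocol XI.E names heart failure from fluid overload as a risk of too much blood. CHF and infections enter secondary composites compared by arm in Table 18.
- Table 31 gives daily lowest Hb by arm, and Table 7 gives off-threshold transfusion by arm.
- The adherence analysis in Protocol XVI.E.5 compares by arm those who change strategy, which may cover post-MI halts. SAP 6.2 has no matching analysis and does not say whether approved halts count.
- Table 8 is a descriptive site-monitoring table with a Total column. It tests nothing, so its Form 4 denominator does not distort any planned comparison.

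All of this stands, and it limits the point to non-serious reactions and the split of approved halts by arm. It does not fill that gap.

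Stronger readings are tempting, and the documents do not support them:

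- That the trial cannot compare reactions between arms. It can: Forms 4 and 8 are collected and the assignment is known. What is missing is a planned table.
- That the liberal strategy's main harm goes unreported. The serious consequences are already shown by arm.
- That a never-transfused participant could be counted in the summed line. Row 3 says the participant was transfused, so this is not shown. The mixed denominator is a fault without it.

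**Conclusion.** The point holds and is minor. The SAP plans no by-arm table of approved halting events, so non-serious transfusion reactions and permitted bleeding-driven transfusion would not be compared between arms, although both are recorded. The summed line in Table 8 is not a coherent proportion.

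The expected size is about 7 to 8 liberal v 1 to 4 restrictive participants with a reaction. This rests on the protocol's 1% and on assumed shares transfused of 90-100% and 10-50%. The 1% covers any possible reaction and is not split by seriousness, so an unknown part of these counts would already be in Table 29. The documents give no rate for rapid bleeding, so its size by arm cannot be estimated. The primary analysis is unaffected.

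**What to change.** Keep the site version of Table 8 for monitoring. Add a version by assigned arm, cited in SAP 6.2 and section 8, with liberal, restrictive and total columns. It should show separately the participants with at least one:

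- adverse reaction during transfusion (Form 4 Q10);
- rapid-bleeding transfusion (Form 4 Q9);
- post-MI halt (Form 8 Q3).

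Give each as n and % of participants randomized, with a second line as % of participants transfused or per unit. Report it descriptively, without a test. Show it to the DMC in closed session during the trial and include it in the final report.

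In both versions, drop the percentage on the line that sums rows 1 to 3, or express it as participants with any of the three events per participant randomized.

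The cost is SAP wording and one table shell, with no new data collection. The drawback is that counts will be small, and some reactions will appear both here and in Table 29, which a footnote can state.

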# of Participants Randomized																	
# of Transfused Units																	
# Transfusion Deviations																	
Transfusion did or did not occur per randomization group Hb threshold																	
Transfusion occurred outside of protocol required window/late																	
Other transfusion deviation not covered by above																	
# of																	

Transfusion Deviations / # of Transfused Units																
Transfusion did or did not occur per randomization group Hb threshold																
Transfusion occurred outside of protocol required window/late																
Other transfusion deviation not covered by above																
# of Participants with Transfusion Deviations																
Transfusion did or did not occur per randomization group Hb threshold																
Transfusion occurred outside of protocol required window/late																
Other transfusion deviation not covered by above																
# of Participants with																

Transfusion Deviations / # Randomized Participants																	
Transfusion did or did not occur per randomization group Hb threshold																	
Transfusion occurred outside of protocol required window/late																	
Other transfusion deviation not covered by above																	

Note: Transfusion did or did not occur per randomization group Hb threshold - Participant assigned to restrictive group was transfused with Hb above 7gm/dL, or participant assigned to liberal group was NOT transfused when Hb below 10gm/dL; Other transfusion deviation not covered by above - Transfusion Protocol deviation not covered by other transfusion-specific deviation codes.

Table 10a-b. Summary of Demographics (ITT, mITT)

Status	Statistics	Liberal Arm (N =)	Restrictive Arm (N =)	Total (N=)	p-value
Age (years) at consent	n				
	Mean (SD)				
	Median				
	Min, Max				
Sex	n				
Male	n (%)				
Female	n (%)				
Ethnicity	n				
Hispanic or Latino	n (%)				
Non-Hispanic or Latino	n (%)				
Unknown	n (%)				
Race	n				
American Indian or Alaska Native	n (%)				

Status	Statistics	Liberal Arm (N =)	Restrictive Arm (N =)	Total (N=)	p-value
Asian	n (%)				
Black or African-American	n (%)				
Caucasian	n (%)				
Native Hawaiian or Pacific Islander	n (%)				
Other	n (%)				
Unknown	n (%)				
Marital Status	n				
Married/Civil Union/Partnership	n (%)				
Never Married	n (%)				
Co-habiting	n (%)				
Divorced	n (%)				
Widowed	n (%)				
Separated	n (%)				
Military Service Branch	n				
Army	n (%)				
Air Force	n (%)				
Coast Guard	n (%)				
National Guard	n (%)				
Navy	n (%)				
Marines	n (%)				
Merchant Marine	n				
Military Service History	n (%)				
World War I	n (%)				
World War II	n (%)				
Korean conflict	n (%)				
Vietnam conflict	n (%)				
Gulf War	n (%)				
Balkan conflict	n (%)				
Afghanistan conflict	n (%)				
Iraq conflict	n (%)				
Peace time	n (%)				
Other	n (%)				

Table 11a-b. Summary of Baseline Assessment (ITT, mITT)

Assessments	Statistics	Liberal Arm (n = ?)	Restricted Arm (n = ?)	All Subjects (N = ?)
Height	n			
	Mean (SD)			
	Median			

	Min, Max			
Weight	n			
	Mean (SD)			
	Median			
	Min, Max			
BMI	n			
	Mean (SD)			
	Median			
	Min, Max			
Heart rate	n			
	Mean (SD)			
	Median			
	Min, Max			
Pre-Op Hb(gm/dl)	n			
	Mean (SD)			
	Median			
	Min, Max			
Pre-Op Albumin	n			
	Mean (SD)			
	Median			
	Min, Max			
Pre-Op Creatinine	n			
	Mean (SD)			
	Median			
	Min, Max			
SBP	n			
	Mean (SD)			
	Median			
	Min, Max			
DBP	n			
	Mean (SD)			
	Median			
	Min, Max			
RCRI Class	n			
	1			
	2			
	3			
	4			

Table 12a-b. Summary of Medical History (ITT, mITT)

Status	Statistics	Liberal Arm (N =)	Restrictive Arm (N =)	Total (N=)	p-value
Hypertension	n (%)				
Hyperlipidemia	n (%)				
Coronary artery disease	n (%)				
Congestive heart failure	n (%)				
COPD or previous active TB	n (%)				
Dementia or current change in mental status	n (%)				
MI within 6 months	n (%)				
Malnourished or cachectic	n (%)				
Cancer or current chemotherapy	n (%)				
Immunodeficiency or infection with HIV	n (%)				
Ischemic stroke or TIA	n (%)				
Prior coronary stent	n (%)				
Cardiac arrhythmias	n (%)				
MI older than 6 months	n (%)				
End stage renal disease	n (%)				
Prior coronary bypass	n (%)				
Diabetes treated with medications (oral hypoglycemic or insulin)	n (%)				
Past smoking	n (%)				
Current smoking	n (%)				

Table 13a-b. Pre-admission Ambulation and Residence (ITT, mITT)

Status	Statistics	Liberal Arm (N =)	Restrictive Arm (N =)	Total (N=)	p-value
Pre-admission Residence	n				
Retirement home	n (%)				
Nursing home	n (%)				
Rehabilitation hospital	n (%)				
Acute care hospital	n (%)				
Own residence	n (%)				
Homeless	n (%)				
Other	n (%)				
Pre-admission Ambulation	n				
Independently ambulatory	n (%)				
Ambulatory with assistance	n (%)				
Wheelchair	n (%)				
Confined to bed	n (%)				

Table 14a-b. Pre-admission Medications (ITT, mITT)

Status	Statistics	Liberal Arm (N =)	Restrictive Arm (N =)	Total (N=)
Pre-admission Medications	n			
Beta Blockers	n (%)			
Insulin	n (%)			
Other Immunosuppressant	n (%)			
Heparin	n (%)			
Diuretics	n (%)			
Oral Hypoglycemics	n (%)			
Prednisone	n (%)			
LMW heparin	n (%)			
Statin	n (%)			
ACE inhibitors	n (%)			
Plavix	n (%)			
Aspirin	n (%)			
Coumadin	n (%)			
Other oral anticoagulant	n (%)			

Table 15a-b. Post-admission Medications (ITT, mITT)

Status	Statistics	Liberal Arm (N =)	Restrictive Arm (N =)	Total (N=)
Post-admission Medications				
Coumadin	n/N (%)			
Day 1 pre-op				
Op day (before or after Op)				
Day 1 post op				
Day 2 post-op				
Discharge day				
Any of the days				

Status	Statistics	Liberal Arm (N =)	Restrictive Arm (N =)	Total (N=)
Heparin Day 1 pre-op Op day Day 1 post op Day 2 post-op Discharge day Any of the day	n/N (%)			
LMW Heparin Day 1 pre-op Op day Day 1 post op Day 2 post-op Discharge day Any of the days	n/N (%)			
Oral Anticoagulant other than Coumadin Day 1 pre-op Op day Day 1 post op Day 2 post-op Discharge day Any of the days	n/N (%)			
Aspirin Day 1 pre-op Op day Day 1 post op Day 2 post-op Discharge day Any of the days	n/N (%)			
Beta-Blocker Day 1 pre-op Op day Day 1 post op Day 2 post-op Discharge day Any of the days	n/N (%)			
Plavix Day 1 pre-op Op day Day 1 post op Day 2 post-op Discharge day Any of the days	n/N (%)			

Status	Statistics	Liberal Arm (N =)	Restrictive Arm (N =)	Total (N=)
Diuretics Day 1 pre-op Op day Day 1 post op Day 2 post-op Discharge day Any of the days	n/N (%)			
ACE Inhibitor Day 1 pre-op Op day Day 1 post op Day 2 post-op Discharge day Any of the days	n/N (%)			
Insulin Day 1 pre-op Op day Day 1 post op Day 2 post-op Discharge day Any of the days	n/N (%)			
Oral Hypoglycemics Day 1 pre-op Op day Day 1 post op Day 2 post-op Discharge day Any of the days	n/N (%)			
Other Immunosuppressant Day 1 pre-op Op day Day 1 post op Day 2 post-op Discharge day Any of the days	n/N (%)			
Prednisone Day 1 pre-op Op day Day 1 post op Day 2 post-op Discharge day Any of the days	n/N (%)			

Status	Statistics	Liberal Arm (N =)	Restrictive Arm (N =)	Total (N=)
Statin	n/N (%)			
Day 1 pre-op				
Op day				
Day 1 post op				
Day 2 post-op				
Discharge day				
Any of the days				

Note: Medications on operation day does not include intraoperative medications

Table 16a-e. Primary Endpoint Analysis (ITT, mITT, No-Recent-Transfusion, Completers, Per-Protocol)

Results	Liberal (n =)	Restrictive (n =)	All Subjects (N=)
	n (%)	n (%)	n (%)
Composite event (Yes)			
Composite event (No)			
Total			
Pearson χ^2 test			
Cochran-Mantel-Haenszel test	(p =) Stratified on Clinical Centers		

Table 17a-e. Primary Endpoint Analysis, Adjusting for Baseline Age, RCRI, and Nadir Hemoglobin (ITT, mITT, No-Recent-Transfusion, Completers, Per-Protocol)

Factors	Coefficients	SE	p-Values (Wald test)	OR (95% C.I.)
Liberal vs Restrictive				
Age				

Factors	Coefficients	SE	p-Values (Wald test)	OR (95% C.I.)
RCRI				
1				
2				
3				
4				
Nadir Hb				

Table 18a-e. Summary of Secondary Outcomes (Except for Length of Stay) (ITT, mITT, No-Recent-Transfusion, Completers, Per-Protocol)

Outcomes	Liberal (N =)	Restrictive (N =)	All Subjects (N=)	χ^2	p-Value
	n (%)	n (%)	n (%)		
90 Day Infectious Complications					
Present					
Absent					
Total					
90 Day Cardiac Complications					
Present					
Absent					
Total					
1 Year All-cause Mortality					
Died					
Alive					
Total					
30 Day all-cause postoperative mortality, MI, coronary revascularization, stroke, or acute renal failure					
Present					
Absent					

Outcomes	Liberal (N =)	Restrictive (N =)	All Subjects (N=)	χ^2	p-Value
	n (%)	n (%)	n (%)		
Total					

Table 19a-e. Secondary Outcomes (Except for Length of Stay), Logistic Regression (ITT, mITT, No-Recent-Transfusion, Completers, Per-Protocol)

Factors	Coefficients	SE	p- Values	OR	OR 99% C.I.	
					Lower	
90 Day Infectious Complications						
Liberal vs Restrictive						
Age						
RCRI						
1						
2						
3						
4						
Nadir Hb						
90 Day Cardiac Complications						
Liberal vs Restrictive						
Age						
RCRI						
1						
2						
3						
4						
Nadir Hb						
30 Day Composite Rate of All-cause Postoperative Mortality, MI, Coronary Revascularization, Stroke, or Acute Renal Failure						
Liberal vs Restrictive						
Age						

Factors	Coefficients	SE	p-Values	OR	OR 99% C.I.	
					Lower	Upper
RCRI						
1						
2						
3						
4						
Nadir Hb						
1 Year All-cause Mortality						
Liberal vs Restrictive						
Age						
RCRI						
1						
2						
3						
4						
Nadir Hb						

Table 20a-e. Summary of Length of Hospital Stay (ITT, mITT, No-Recent-Transfusion, Completers, Per-Protocol)

Intervention	Length of Hospital Stay		p-Values
	Median	Lower Quartile, Upper Quartile	
Liberal Arm			
Restrictive Arm			
Overall			

Table 21a-e. Quantile Regression for Length of Hospital Stay (ITT, mITT, No-Recent-Transfusion, Completers, Per-Protocol)

Factors	Coefficients, SEs and p Values		
	25 th	Median (50 th)	75 th

Intercept				
Liberal vs Restrictive				
Age				
RCRI				
1				
2				
3				
4				
Nadir Hb				

Table 22a-e. Summary of Transfusion Related Individual Components of the Composite Endpoint (ITT, mITT, No-Recent-Transfusion, Completers, Per-Protocol)

Outcomes		Liberal	Restrictive	All Subjects	χ^2	p-Value
		(N =)	(N =)	(N=)		
90-day all-cause mortality	Present					
	Absent					
	Total					
90-day MI	Present					
	Absent					
	Total					
90-day coronary revascularization	Present					
	Absent					
	Total					
90-day stroke	Present					
	Absent					
	Total					
90-day acute renal failure	Present					
	Absent					
	Total					

Table 23a-e. Transfusion Related Individual Components of the Composite Endpoint, Logistic Regression (ITT, mITT, No-Recent-Transfusion, Completers, Per-Protocol)

	Outcomes	Coefficients	SE	p-Value	OR	OR 99% C.I.	
						Lower	Upper
90-day all-cause mortality	Liberal vs Restrictive						
	Age						
	RCRI						
	1						
	2						
	3						
	4						
	Nadir Hb						
	Transfusion and Age						
	Liberal vs Restrictive						
90-day MI	Age						
	RCRI						
	1						
	2						
	3						
	4						
	Nadir Hb						
	Liberal vs Restrictive						
	Age						
	RCRI						
90-day coronary revascularization	1						
	2						
	3						
	4						
	Nadir Hb						
	Liberal vs Restrictive						
	Age						
	RCRI						
	1						
	2						
90-day stroke	3						
	4						
	Nadir Hb						
	Liberal vs Restrictive						
	Age						
	RCRI						
	1						
	2						
	3						
	4						

	Outcomes	Coefficients	SE	p-Value	OR	OR 99% C.I.	
						Lower	Upper
90-day acute renal failure	Liberal vs Restrictive						
	Age						
	RCRI						
	1						
	2						
	3						
4							
	Nadir Hb						

Tables 24a-e. Effect of Age of Blood Transfused on Primary Outcome (ITT, mITT, No-Recent-Transfusion, Completers, Per-Protocol)

Factors	Coefficients	p-Values (Wald test)	OR (95% C.I.)
Using oldest unit transfused			
Age of Blood Transfused			
Liberal vs Restrictive			
Baseline Age of Participant			
RCRI			
1			
2			
3			
4			
Nadir Hb			
Using mean age of all the units transfused			
Age of Blood Transfused			
Liberal vs Restrictive			
Baseline Age of Participant			
RCRI			
1			
2			

3			
4			
Nadir Hb			

Tables 25a-e. Effect of Age of Blood Transfused on 90-day Wound Infection (ITT, mITT, No-Recent-Transfusion, Completers, Per-Protocol)

Factors	Coefficients	p-Values (Wald test)	OR (99% C.I.)
Using oldest unit transfused			
Age of Blood Transfused			
Liberal vs Restrictive			
Baseline Age of Participant			
RCRI			
1			
2			
3			
4			
Nadir Hb			
Using mean age of all the units transfused			
Age of Blood Transfused			
Liberal vs Restrictive			
Baseline Age of Participant			
RCRI			
1			
2			
3			
4			
Nadir Hb			

Tables 26a-e. Effect of Age of Blood Transfused on 90-day Pneumonia (ITT, mITT, No-Recent-Transfusion, Completers, Per-Protocol)

Factors	Coefficients	p-Values (Wald test)	OR (99% C.I.)
Using oldest unit transfused			
Age of Blood Transfused			
Liberal vs Restrictive			
Baseline Age of Participant			
RCRI			
1			
2			
3			
4			
Nadir Hb			
Using mean age of all the units transfused			
Age of Blood Transfused			
Liberal vs Restrictive			
Baseline Age of Participant			
RCRI			
1			
2			
3			
4			
Nadir Hb			

Table 27a-e. Cox Regression Model for Primary Endpoint (ITT, mITT, No-Recent-Transfusion, Completers, Per-Protocol)

Factors	Coefficients	S.E.	p-Values (Wald test)	HR (95% C.I.)
Liberal vs Restrictive				
Age				
RCRI				
1				
2				
3				
4				
Nadir Hb				

Table 28a-e. Cox Regression Model for Secondary Endpoints (ITT, mITT, No-Recent-Transfusion, Completers, Per-Protocol)

Factors	Coefficients	S.E.	p-Values (Wald test)	HR (99% C.I.)
90 Day Infectious Complications				
Liberal vs Restrictive				
Age				
RCRI				
1				
2				
3				
4				
Nadir Hb				
90 Day Cardiac Complications				
Liberal vs Restrictive				
Age				

Factors	Coefficients	S.E.	p-Values (Wald test)	HR (99% C.I.)
RCRI				
1				
2				
3				
4				
Nadir Hb				
30 Day Composite Rate of All-cause Postoperative Mortality, MI, Coronary Revascularization, Stroke, or Acute Renal Failure				
Liberal vs Restrictive				
Age				
RCRI				
1				
2				
3				
4				
Nadir Hb				
1 Year All-cause Mortality				
Liberal vs Restrictive				
Age				
RCRI				
1				
2				
3				
4				
Nadir Hb				

Table 29. Cumulative SAE Incidence by Treatment Group using MedDRA Coding in Randomized Participants, by Body System and Preferred Term (Safety)

	Liberal Arm (n=)			Restrictive Arm (n=)			All Subjects (N=)		
	Participants			Participants			Participants		
Body System and Preferred Term	N	(%)	Events	N	(%)	Events	N	(%)	Events
All Serious Adverse Events									
Infections and infestations									
Wound infection									
Sepsis									
... and so on									

Table 30. List of SAEs where Death of Randomized Participant Is Indicated (Safety)

Center	Ppt	Intervention Group	1. Start Date (date the SAE began)	Date of Death	Original SAE Attribution to Study	Detailed description of event
...						

Table 31. Summary of Laboratory Assessment (Safety)

Time	Assessments	Statistics	Liberal Arm	Restricted Arm	All Subjects
------	-------------	------------	-------------	----------------	--------------

			(n = ?)	(n = ?)	(N = ?)
